6.2 PREPARATION/HANDLING/STORAGE/ACCOUNTABILITY

6.2.1 ACQUISITION AND ACCOUNTABILITY

The study intervention and control products were originally purchased from Photo Therapeutics. There is no distribution plan as the treatment and mock devices are already in the possession of the research team (previously purchased for the Phase I studies). Disposal of unused product is not applicable to this protocol.

6.2.2 FORMULATION, APPEARANCE, PACKAGING, AND LABELING

The LED light source is the Omnilux new-U (GlobalMed Technologies, Glen Ellen, CA) handheld LED phototherapy device, which is commercially available and FDA cleared for treatment of periorbital wrinkles. The device contains an array of LEDs with a transparent lens cover, a ventilation fan, a three-position switch, and a connection socket. The LED has a 4.7 cm x 6.1 cm rectangular aperture and emits visible red light (633 nm \pm 6 nm) at a power density of 360.2 W/m² at room temperature.

The mock therapy device has a ventilation fan and functional resistors designed to sound, look, and feel similar to the phototherapy treatment device, but emits no irradiation.

6.2.3 PRODUCT STORAGE AND STABILITY

The phototherapy treatment and mock therapy devices will be stored at room temperature in a secured private clinic examination room, avoiding extreme temperatures and direct sunlight.

6.2.4 PREPARATION

The treatment and mock devices are powered by wall power supply plugged into an AC electrical outlet. The operator (i.e., investigators) will flip the selector switch to turn on the red LEDs and place the transparent lens in close contact with the treatment area, at a maximum of 1 cm from the skin surface.

6.3 MEASURES TO MINIMIZE BIAS: RANDOMIZATION AND BLINDING

Treatment Dose Randomization

A block randomization scheme will be used for balanced allocation of subjects to study arms, such that 10 subjects are assigned to each treatment group. All subjects will be randomized as they are enrolled

(i.e., sequentially in blocks of three). Study enrollment concludes when a total of 30 subjects have been randomized.

For the first subject who enrolls, Arabic numeral "1", "2", or "3" will be generated at random using a computer-based randomization tool (*www.randomizer.org*). This subject has a 1 in 3 chance of being assigned to any of the three treatment groups: "1" for Group 1 (LED-RL 160 J/cm²), "2" for Group 2 (LED-RL 320 J/cm²), or "3" for Group 3 (LED-RL 480 J/cm²). The next subject who enrolls is then similarly randomized to one of the remaining two treatment groups, and the following subject who enrolls is automatically assigned to the last treatment group. This block randomization process continues until each treatment group is filled with 10 subjects.

Split-Face Randomization

Within each treatment group, the treatment side (right face versus left face) will be determined using a computer-generated randomization tool (*www.randomizer.org*). The assignment to a treatment dose and a treatment side of the face occurs simultaneously. Within each treatment group, a single set of Arabic numerals "0" to "9" will be generated, resulting in a random sequence of 10 numerals for sampling without replacement. As subjects are allocated to a treatment group, they are assigned to a numeral in this set based upon their order of enrollment. In other words, the first subject to enroll in a treatment group is assigned to the first random numeral, the second subject to the second random numeral, etc. Subjects assigned to even numerals will receive LED-RL phototherapy on the right side of the face, making the left face the control. Subjects assigned to odd numerals will receive LED-RL phototherapy on the left side of the face, making the right face the control. Within each treatment group (n=10), 5 subjects will receive treatment on the right face and the other 5 subjects will receive treatment on the left face.

Blinding

This is a single-blind study wherein the subjects are blinded to the treatment side. From the subject's perspective, the LED-RL phototherapy device and the mock therapy device are indistinguishable since 1) the treatment area is outside of their range of view and 2) the mock therapy device was designed to simulate the actual treatment device in terms of appearance, sound, and feel.

Clinicians involved in evaluating certain outcome measures (e.g., histology, POSAS, evaluation of digital photography) will be also be blinded to the treatment side. This includes the following clinicians.

- The investigator who will perform the POSAS, a subjective scar assessment scale that is scored based on clinical judgment [name]
- The expert panel of two independent dermatologists charged with photographic evaluation of the scars [name] and [name]
- The dermatopathologist examining the skin specimen slides [name]

The PI and research coordinator will be aware of the trial randomization codes. Unblinding may occur at the discretion of the PI. For example, the occurrence of a SAE may necessitate knowledge of the treatment side so that the subject may receive appropriate medical care. In the event of inadvertent unblinding of blinded investigators or collaborators, the data point for the outcome measure affected by the unblinding will be considered invalid. For example, if the investigator performing the POSAS inadvertently gains knowledge of the treated side, that POSAS score will be invalid and excluded from

statistical analyses due to potential bias. Intentional and unintentional breaking of the blind should be reported to the PI.

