Physical risks of the proposed LED-RL phototherapy include potential toxicity and lack of efficacy. There is low risk of infection as we will not treat non-intact skin (since presence of open wound(s) at the treatment site is an exclusion criterion) and all LED-RL phototherapy devices will be cleaned with disinfectant before and after each treatment session. Common expected post-treatment effects include mild erythema (redness), warmth, and swelling that is transient (i.e., lasts less than 24 hours). Subjects may have tenderness or swelling at the treatment site. Since darker skin pigment absorbs more light energy in the epidermis, it is possible that subjects with darker skin types may experience a greater sensation of epidermal warmth, textural changes, or dyspigmentation. Due to the split-face study design (i.e., only one surgical incision receives LED-RL phototherapy), there is a possibility of uneven cosmetic results of the scar appearances at the conclusion of the study. That is, the scar on one side of the face may look better, worse, or the same as the scar on the other side.

Potential serious adverse events including, but not limited to, second-degree or higher skin burning, blistering, persistent swelling, persistent pain, ulceration, change in sensation, mucle weakness, or worsening of surgical scar will be monitored and the trial will be halted early if necessary. While we have tested the effects of LED-RL on fibroblasts, it is not known whether LED-RL alters the function of other cell types *in vivo*. At the doses studied, there may be inhibitory effects on other cells found in the epidermis and dermis such as keratinocytes, melanocytes, endothelial cells, neurons and immune cells. Due to the location of LED-RL phototherapy on the face, there is a theoretical risk of neurological side effects such as headaches, malaise, fatigue, and change in hearing.

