The treatment side (right face versus left face) will also be randomized to control for effects of uneven sun exposure. The untreated side will receive mock therapy with sham irradiation via a mock device that looks, sounds, and feels similar to the treatment device, but does not produce light. Subjects will

be blinded to the LED-RL device versus mock device as the treatment site is outside of their range of view and they will wear safety goggles.

Beginning scar reduction therapy at 1 week after surgery (defined as POD 4 to POD 8) is a validated intervention time point for limiting surgical scars.¹ Subjects will receive their treatment sessions inoffice three times weekly, a standard phototherapy regimen,^{73–75} starting at 1 week post-surgery for a total of nine treatment sessions. This treatment schedule (frequency and duration) is identical to the schedules used in our Phase I studies. Each treatment session will be observed by an investigator to monitor for any adverse events and to ensure safety and adherence.

During the study, subjects will be asked to avoid scar treatments to both periauricular incision sites. Scar treatment options include, but are not limited to, silicone gels/sheets, intralesional corticosteroids, 5-fluorouracil, laser therapy, radiotherapy, cryotherapy, bleomycin, mitomycin C, imiquimod, pressure therapy, adhesive microporous hypoallergenic paper tape, onion extract, massage therapy, over-the-counter topical emollients for scars, laser therapy, and surgical revision.⁷⁶ As described above, subjects will be counseled on proper wound care during the postoperative period to facilitate appropriate wound healing. Refer to *Section 10.2: Additional Considerations* for a discussion of available scar treatments at the conclusion of the study.

Following the study intervention period, subjects will have follow-up assessments on approximately POD 30, 90, and 180. At each follow-up visit, scar characteristics will be recorded objectively and subjectively through skin elasticity and induration measurements, tissue histology, photographic evaluation, skin imaging analysis, collagen and water concentration measurements, OCT, and standardized patient and observer assessments as described in *Section 3: Objectives and Endpoints* and *Section 8: Study Assessments and Procedures*.

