6 STUDY INTERVENTION

6.1 STUDY INTERVENTION(S) ADMINISTRATION

6.1.1 STUDY INTERVENTION DESCRIPTION

The LED light source is the Omnilux new-U handheld LED phototherapy device, which is commercially available and FDA-cleared for the treatment of periorbital wrinkles. This device has not been approved or cleared for the indications the protocol is designed to investigate (skin fibrosis). The device has a 3-position switch that allows the user to select the red light output (switch down).

The mock therapy device emits no irradiation. The mock therapy device has a ventilation fan and functional resistors designed to sound, look, and feel (i.e., temperature matched) similar to the phototherapy treatment device, but does not emit LED-RL.

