The Omnilux new-U has been tested to international standards to ensure that its outputs are safe for the eyes. However, subjects will wear safety goggles during the treatment sessions, as recommended by the manufacturer for patient comfort.

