8.2 SAFETY AND OTHER ASSESSMENTS

Refer to *Section 1.3: Schedule of Activities*, for the sequence of events that should occur during the screening process.

Study Specific Procedures and Evaluations for Safety or Other Purposes

- The subject's medical history will be obtained by interview at the screening visit to screen for exclusion criteria.
- The subject's concomitant medication list will be reviewed at each study visit to screen for prohibited medications.
- A screening photosensitivity test will be conducted prior to enrollment, wherein the potential subject will be exposed to LED-RL for 20 minutes on the non-dominant upper forearm (as recommended by the manufacturer in the Omnilux new-U user guide), and then evaluated 24 hours later for evidence of photosensitivity. Criteria for photosensitivity include, but are not limited to: warmth, erythema, edema, blistering, rash, pain, or discomfort lasting more than 24 hours. If no adverse events occurred, the potential subject is deemed "non-photosensitive" and thus eligible for participation in the study.
- At the screening visit, the mini-facelift surgery will be discussed with the subject, including details of the procedure, risks, benefits, alternative options, expected outcomes, and pre- and post-operative instructions.
- The mini-facelift surgery will be performed in-office under local anesthesia by [name] (co-investigator and board-certified dermatologic surgeon).
- A targeted physical examination of the treatment sites (i.e., the periauricular skin and surrounding areas) will be performed at each study visit.
- Each treatment session will be monitored for any safety issues or adverse events, either reported by the subject or observed by the investigator.
- Subjects will be provided with a daily diary to record any adverse events experienced at home during the 3-week treatment period. Investigators will call subjects on a weekly basis to monitor for adverse events during the same time period.
 - Common expected post-treatment effects of transient (i.e., lasts less than 24 hours) erythema, warmth, or edema at the treated sites will be recorded. However, any occurrence of these expected effects will not be considered an adverse event in safety data reports, unless the effect lasts more than 24 hours or is considered serious.
- An exit questionnaire will be administered at the final study visit to assess for patient-reported outcomes and elicit other feedback.

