8.3.5 ADVERSE EVENT REPORTING

All required reportable events must be reported to the IRB within the deadlines specified in the SUNY Downstate Medical Center Policy IRB-01: Human Research Protections Program. Unanticipated adverse device effects (UADEs) will be reported as soon as possible, but no later than 10 days.

Any AEs that occur in-office during or immediately after treatment sessions, or reported by the subject in the AE diary or in weekly phone calls, will be captured on the appropriate CRF. Information to be collected includes a description of the AE, time of onset, severity, relationship to the study intervention, and time of resolution/stabilization.

Subjects will be counseled regarding the expected outcome of skin erythema and warmth, found to resolve within 24 hours in other clinical studies and occurs in 10% of participants.^{70,71} For this study, the common expected post-treatment side effects of transient erythema, warmth, and swelling at the treated sites will be recorded, but will not be considered an AE for the purposes of safety reports.

All AEs will be reported to the designated medical monitor ([name]), independent safety monitor ([name]), and internal faculty committee at monthly meetings. Please refer to *Section 10.1.6: Safety Oversight* for the composition of the internal committee. [name] is the Director of Clinical Trials & Research in the Department of Dermatology at SUNY Downstate whose responsibilities include: managing and ensuring research compliance; monitoring all departmental clinical trials for AEs; and overseeing appropriate reporting of AEs to the IRB. AEs will be reported to the IRB, NIH, and FDA on a quarterly basis. The PI is responsible for completing and signing off on the AE reports.

[figure not shown]

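### Subject blinding to the treated side is asserted in section 6.3 but neither assured nor checked, which matters for the patient-rated POSAS

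*Combined protocol and SAP*

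**What the plan says.** Section 6.3 describes a single-blind trial in which subjects do not know the treated side. It states that to them "the LED-RL phototherapy device and the mock therapy device are indistinguishable since" the treated area is out of sight and the mock was built to imitate the real device.

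Other sections describe how this is meant to work:

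- **View.** Section 4.1 says that the treatment site is "outside of their range of view and they will wear safety goggles". Section 6.1.2 gives the purpose of the goggles: "subjects will wear safety goggles during the treatment sessions, as recommended by the manufacturer for patient comfort".
- **Mock device.** Section 4.1 describes "a mock device that looks, sounds, and feels similar to the treatment device, but does not produce light". Section 6.1.1 adds that it is "designed to sound, look, and feel (i.e., temperature matched) similar to the phototherapy treatment device, but does not emit LED-RL".
- **Administration.** Sections 6.1.2 and 6.2.4 have both devices running together, one on each side. The lens is transparent and may be up to 1 cm from the skin. Sessions last 30, 60 or 90 minutes by dose group, and there are nine of them.
- **After-effects.** Section 2.3.1 lists short-lived erythema, warmth and swelling among the expected effects of LED-RL and anticipates no physical risk from the mock. Section 8.3.5 says: "Subjects will be counseled regarding the expected outcome of skin erythema and warmth", and puts the frequency in other studies at 10% of participants. Section 8.2 says: "Subjects will be provided with a daily diary to record any adverse events experienced at home".
- **Outcome.** Section 8.1 has the subject score six POSAS items at POD 30, 90 and 180. Section 9.4.3 reports secondary outcomes as medians and ranges, without inference.
- **Safeguards.** Section 6.3 invalidates a data point when a blinded investigator or collaborator learns the side, and asks that any break of the blind be reported to the PI. It has no invalidation rule for the subject as rater, and no section asks subjects which side they believe was active.

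**The concern.** In a split-face trial the subject scores both of their own scars. Someone who has worked out which side was lit may score that side more kindly, and the side difference then carries expectation as well as effect. The patient half of POSAS covers itch, pain, stiffness, colour, relief and thickness, all of which are judgements. Section 3 gives weight to the patient's own view as a reason for choosing the scale.

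The plan rests this blind on the design of the devices and never checks it. If the blind leaks, the patient scores would still be reported as blinded and a reader could not tell. Reporting them descriptively does not remove that problem.

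**Working it through.** No sample size, power or error rate in the plan depends on this point, so there is no stated figure to reproduce. The check sets each support for the blind against what the documents say, then sizes the one cue for which they give a rate.

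**1. Light.** Sections 4.1, 6.1.1 and 6.2.2 agree that the mock emits none, so only one side of the face is lit. Placing the aperture out of view limits what is seen directly but does not exclude a glow on one side. The goggles would close that gap if they blocked red light. The stated reason for wearing them is comfort, and their opacity is not given. Subjects may also have a reference for the real device: section 8.2 gives each one 20 minutes of LED-RL on the forearm at screening, and does not say that it is hidden.

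**2. Heat during a session.** Section 6.1.1 says the mock is temperature matched, so heat from the device is addressed. Section 2.3.1 says "it is possible that subjects with darker skin types may experience a greater sensation of epidermal warmth". That describes a possible response of the skin to absorbed light, and the documents do not say whether the matching reproduces it.

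**3. After-effects at home.** Out-of-view placement works only during the session. Erythema, swelling or a blister can be seen or felt later. Subjects are told to expect erythema and warmth, and they keep a daily diary.

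Inputs: 30 subjects, 10 per dose group (6.3); 10% of participants with erythema and warmth (8.3.5). Assumptions: the reaction occurs on the LED side only, and subjects are independent.

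- Expected number: 30 × 0.10 = 3.0 overall; 10 × 0.10 = 1.0 per dose group.
- At least one of 30: 1 − 0.90^30 = 0.958.
- At least one of 10: 1 − 0.90^10 = 0.651.

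The 10% may not carry over to this trial. Section 8.3.5 attributes it to the same two studies that section 4.1 cites for the 160 J/cm² starting dose, and 20 of the 30 subjects receive 320 or 480 J/cm². An assumed range gives:

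| Rate | Expected of 30 | At least one of 30 |
|---|---|---|
| 5% | 1.5 | 0.785 |
| 10% | 3.0 | 0.958 |
| 20% | 6.0 | 0.999 |
| 33% | 10.0 | > 0.999 |

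The top row value of 33% borrows the Phase I blister count at 480 J/cm² (1 of 3). That is a different event, so it marks an upper end for illustration only.

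**4. What a guess question could show.** Suppose 10% of subjects have a decisive cue and the rest guess at 50%. The expected share correct is 0.10 + 0.90 × 0.50 = 0.55, or 30 × 0.55 = 16.5 subjects against 15 by chance. A table of guesses in 30 subjects could therefore reveal a gross leak, such as visible light, but could not confirm that a few subjects were not cued.

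**The case against.** The case on the other side is substantial, and most of it stands.

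- **The plan does take blinding of subjects seriously.** The mock has a fan and resistors, is temperature matched, and sits out of view close to the skin. A reader might infer that only the LED side can feel warm. The documents do not support that, given section 6.1.1.
- **One-sided redness is not proof of the LED side.** Both sides are recent incisions, both are cleaned with alcohol, and section 2.3.1 lists swelling and discoloration as surgical risks. The absence of mock adverse events in Phase I does not settle it, because that work was on normal skin.
- **Silence about goggle opacity is not evidence of a leak.** A reader might infer that spilled light unblinds everyone. No figure supports this, and it does not justify added hardware around the devices.
- **The 10% is per participant.** A reader might compound it over nine sessions to reach a much larger number. Section 8.3.5 gives no per-session rate.
- **The outcome is limited.** Patient POSAS is one part of a secondary measure. With about one cued subject in a group of 10, a median would move little. No analysis of patient POSAS by skin type is planned, since section 9.4.7 concerns pliability.
- **The effects fade within 24 hours**, well before POD 30.

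Two things remain. Knowledge of the side can outlast the redness that gave it away. And section 6.3 states the blind as a fact, with no check behind it.

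**Conclusion.** Blinding of subjects to the treated side is asserted but not assured. That only one device emits light, that both run together, and that the goggles are specified for comfort are all in the text. The expected after-effects add a cue for about 3 of 30 subjects at the protocol's own rate (1.5 to 10 over the assumed range), if they occur on the LED side only. The contribution of visible light cannot be sized from the documents, and neither can any shift in POSAS scores.

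A reader might go further and conclude that the patient POSAS is unblinded. The documents do not support that: at 10%, most subjects would have no after-effect cue, and the mock addresses look, sound and device heat.

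The point is confined to patient-rated POSAS. The instrument-measured primary endpoint, the observer POSAS and the photograph VAS are not part of it. It is a cheap improvement, not a flaw that threatens the trial's main result.

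**What to change.** 1. In 6.1.2 and 6.3, require eyewear that blocks visible light during sessions, the same for all subjects, while still meeting the manufacturer's recommendation.
2. In 6.3, replace *indistinguishable* with *designed to be similar*.
3. At Visit 10, before the POD 30 POSAS, ask each subject which side they think had the active light: left, right or don't know.
4. In 9.4.3, tabulate the guesses (correct, wrong, don't know) by dose group, and describe the patient POSAS as blinded only with that table alongside. Treat the table as descriptive and set no pass mark.

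The cost is slightly different eyewear, one question at an existing visit and one small table. Visits, sample size and the primary analysis are unchanged. The downside is that a guess may partly reflect perceived effect, and at this size it can expose a gross failure of the blind but cannot prove that the blind held. Asking before the follow-up scoring limits the first problem.

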We do not anticipate any physical risks of the mock irradiation since it does not generate light and there were no adverse events associated with the mock treatment device in the Phase I studies. However, due to the split-face study design, subjects may have uneven cosmetic results between the two periauricular incision sites. The scar on one side of the face may appear better, worse, or the same as the scar on the contralateral side, depending on the effects of the study intervention. A proposed component of this study is optional skin biopsies for histological examination. Though a skin biopsy is a generally safe procedure, potential risks include bleeding, bruising, scarring, pain, skin sensitivity, and infection.

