- Antera 3D (Miravex, Dublin, Ireland) is a novel skin imaging analysis device that uses reflectance mapping of different wavelengths to acquire three-dimensional images of the skin surface and objectively measures multiple skin dimensions. It accurately measures wrinkles, texture, scars, skin color, redness, and pigmentation. The software also compares images to enable progress tracking and assess therapeutic efficacy. ^{67,68}
 - Alternatively, the Cherry3 camera (Cherry Imaging, Yokneam, Israel) is a new stereoscopic optical and high-resolution 3D imaging system that is specifically designed to objectively measure changes in above-surface scar volume after various interventions. It has been shown to be valid, accurate, and practical for assessing scar volume and for monitoring treatment response.⁶⁹
- Skin specimens will be obtained via optional 2 mm punch biopsy on POD 0 (prior to surgery) and POD 30 (first follow-up visit after completion of LED-RL treatment). All optional skin biopsies will be perform by [name] or [name]. Skin specimens will be used for histological analysis and molecular studies.
 - After skin biopsy, the sample will be placed in fixative (10% neutral buffered formalin) for routine tissue processing and embedding. Paraffin embedded sections will be mounted on glass slides and stained with hematoxylin and eosin (H&E) and either Masson's trichrome or picrosirius red for evaluation of collagen. Histological examination of skin specimens will be conducted to quantify the number of Ki-67 positive fibroblasts and to qualify collagen content.⁷⁷
 - High-throughput assays will be performed using subject biopsy specimens to screen for molecular effects associated with LED-RL treatment. Molecular testing will include RNA-Seq, microRNA arrays, and quantitative real-time PCR (RT-PCR).
- Subjective scar evaluations using the Patient and Observer Scar Assessment Scale (POSAS) will be performed by the same blinded investigator (the treating surgeon) in conjunction with the subject at follow-up visits on POD 30, 90, and 180.

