9.4.1 GENERAL APPROACH

In initial intention-to-treat analyses, all available data will be included. Multiple imputation will be used where dependent variable values are missing. In subsequent per-protocol analyses, only subjects with complete data will be included.

SAS (SAS Institute, Cary NC) 9.4 statistical software will be used.

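### Deleting ratings after inadvertent unblinding may be an informative exclusion; keep and flag them, and tabulate the assessor-rated outcomes with and without them.

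*Combined protocol and SAP*

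**What the plan says.** Section 6.3 sets a general rule: after inadvertent unblinding of a blinded investigator or collaborator, "the data point for the outcome measure affected by the unblinding will be considered invalid". Its worked example is the POSAS: "if the investigator performing the POSAS inadvertently gains knowledge of the treated side, that POSAS score will be invalid and excluded from" the statistical analyses. The blinded clinicians listed there are the POSAS investigator, the two-dermatologist photograph panel and the dermatopathologist.

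The same section lets the PI unblind deliberately, for example because "the occurrence of a SAE may necessitate knowledge of the treatment side so that the subject may receive appropriate medical care". No data rule is attached to that case.

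Under Section 8.1 the POSAS assessments "will be performed by the same blinded investigator (the treating surgeon) in conjunction with the subject at follow-up visits on POD 30, 90, and 180".

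On what each side of the face may show, Section 2.3.1 states of the control: "We do not anticipate any physical risks of the mock irradiation since it does not generate light", and adds that "there were no adverse events associated with the mock treatment device in the Phase I studies". For LED-RL it foresees transient redness, warmth and swelling, possible textural or pigment change in darker skin, and, among potential serious events, burns, blistering, ulceration and a worse surgical scar. Section 4.3 regards blistering as likelier at higher fluences, but mild and without lasting effect.

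On analysis, Section 9.4.1 says "In initial intention-to-treat analyses, all available data will be included". Section 9.4.3 reports secondary outcomes as medians and ranges without tests. No section plans a count of voided scores, a listing of causes or a sensitivity table.

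**The concern.** Voiding a score because the rater learned the side is an exclusion made after randomisation, and its trigger can depend on treatment. Only one side receives light, so a light-type reaction on one side is a clue to the allocation. If the subjects whose reactions give the side away also have worse LED-side scars, deleting their scores removes unfavourable results, and the reader of the tables cannot see that it happened.

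The rule is also incomplete. It voids one score, but the same surgeon rates the next visits and cannot unlearn the side. It covers inadvertent unblinding only, so a score given after deliberate unblinding has no stated status. It does not say whether the patient's half of the POSAS falls with the observer's. Two analysts could build different datasets from the same text.

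At stake are the observer POSAS, the photographic VAS and the histology. Section 9.1 attaches the secondary efficacy hypothesis to POSAS and VAS, although Section 9.4.3 tests neither.

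**Working it through.** The plan gives no figure for unblinding or voided scores, so there is none to reproduce. The only planned number used here is 10 subjects per arm (Section 9.2: 9 / (1 − 0.10) = 10).

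**1. Could a reaction still be visible when the POSAS is scored?** Treatment starts at POD 4 to 8. On the Monday/Wednesday/Friday pattern of the sample schedule, the ninth session comes 18 days after the first: 4 + 18 = 22 to 8 + 18 = 26. The first follow-up is POD 30 ± 7 days, that is, POD 23 to 37. The visit can therefore fall within days of the last session. POD 90 and 180 cannot; there, only a lasting change such as altered pigment, or what the surgeon already knows, could matter.

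**2. How many scores might be lost?** Phase I saw a blister in 1 of 3 subjects at 480 J/cm². If 1 to 3 of the 10 subjects in that arm unblind the surgeon (assumed), 10% to 30% of its observer scores at a visit are lost.

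**3. Shift in the mean.** Let p be the share of an arm whose reaction unblinds the rater, and d the points by which their LED-minus-mock difference is worse than that of the others (higher POSAS is worse). If the others average m, the full mean is m + p × d and the mean after exclusion is m. The shift is −p × d.

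| p | d (points) | shift in mean | shift in median (simulated) |
|---|---|---|---|
| 0.10 | 3 | −0.30 | −0.29 |
| 0.20 | 6 | −1.20 | −1.09 |
| 1/3 | 10 | −3.33 | −2.95 |

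The medians come from 100,000 simulated arms of 10, with an assumed SD of the difference of 5 points, m = 0, and every reactor unblinding the rater. All values of d are assumed. The p values are a range suggested by the 10% transient-reaction rate in Section 8.3.5 and the 1-in-3 blister count; neither is a rate of unblinding. At d = 0 the shift is 0.

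**4. If benefit also unblinds.** Suppose a share q is dropped because the LED side is visibly better, by the same d. The shift becomes −(p − q) × d. With d = 6:

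- p = 0.20, q = 0.10: −0.6
- p = q = 0.20: 0
- p = 0.10, q = 0.20: +0.6, against LED-RL

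**5. An assumed single-arm illustration.** Give every unaffected subject a difference of −3 and every affected subject +6.

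- One affected: (9 × −3 + 1 × 6) / 10 = −2.1
- Three affected: (7 × −3 + 3 × 6) / 10 = −0.3
- After exclusion: −3.0 in both cases

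The upper end of the range falls from +6 to −3. The median is −3 before and after. Both of these last results arise because all unaffected subjects share one value; with spread, as in step 3, the median moves nearly as far as the mean.

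**The case against.** A reader might infer that subjects with a visible LED-side reaction lose their scores and that the remaining results therefore favour LED-RL. The documents do not support that as a statement of fact.

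- The trigger in Section 6.3 is knowledge of the side, gained inadvertently. Nothing says that a visible reaction, or a suspicion based on one, counts. The SAE sentence concerns deliberate unblinding and carries no exclusion.
- The research coordinator gives the treatment and watches for reactions (Section 6.1.2). The documents do not say that the surgeon sees complications between POSAS visits. Expected effects last less than 24 hours, and a healed blister need not worsen a scar score.
- Surgery itself can cause swelling, discolouration or necrosis on either side (Section 2.3.1), so a one-sided change is not proof of allocation.
- Visible benefit could also reveal the side, which would offset or reverse the direction.
- Three Phase I subjects fix no rate, as Sections 4.1 and 4.3 acknowledge.

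All of this stands, and it makes the direction conditional. It does not remove the possibility of informative loss, the silence on later scores or the absence of reporting.

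The rule also has a real purpose: voiding a subjective score from a rater who knows the side guards against detection bias. And a voided score can be read as no longer available, so Sections 6.3 and 9.4.1 are in tension rather than in plain contradiction.

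Existing safeguards help only in part. Breaks of the blind go to the PI, adverse events are tabulated by dose group (Section 9.4.4) and individual data are listed (Section 9.4.8), but nothing links a break to a voided score. Multiple imputation under Section 9.4.1 is not a clear rescue. Section 9.4.2 uses the term dependent variable for the two pliability measures, and imputation that ignored the reaction would not remove the bias.

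**Conclusion.** The exclusion in Section 6.3 may be informative, and the plan offers no way to see whether it was. It may favour LED-RL if LED-side reactions with worse scars cause the unblinding, and may disfavour it if evident benefit does. Under the first assumption, with every reactor unblinding the rater, the shift in the mean POSAS difference runs from about 0.3 to 3.3 points on a subscale scored 6 to 60. It is zero if reactors score no worse or if the two routes balance. Because Section 4.3 expects blistering mainly at higher fluences, losses could concentrate in the 480 J/cm² arm, where each lost score is 10% of the arm.

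The reach is limited to the observer POSAS, VAS and histology, all reported descriptively. The VAS panel works from photographs, independently of the surgeon, so its exposure is smaller. The primary endpoint is measured by instrument, its operators are not among the blinded raters listed in Section 6.3, and neither it nor its analysis is touched. This is worth amending but does not threaten the main result.

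**What to change.** Amend Section 6.3 along these lines:

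> Ratings made after a rater has been unblinded, inadvertently or deliberately, stay in the dataset and are flagged with the date and cause of unblinding. The flag carries forward to all later ratings of that subject by the same rater. Observer and patient POSAS subscales are flagged separately.

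Add to Section 9.4.3 that the POSAS, VAS and histology tables are shown with and without flagged ratings, together with counts of flagged ratings by dose group and cause. Where the surgeon was unblinded, show the independent panel's photographic VAS for the same visit alongside; those photographs are already taken. One cross-reference in Section 9.4.1, stating that flagged ratings count as available data, removes the tension between the two sections.

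The cost is a protocol wording change, one CRF flag and one repeated set of tables. The small downside is that one version of each table holds a few scores from a rater who knew the side; the other version exposes their influence. Which version is called the main one is a judgement between detection bias and selective loss, and should be fixed before any unblinded data are seen. No visit, procedure or clinical rule changes.
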